The study primary outcome measure was defined as the change in total combined inches in circumference measurements (hips, waist and upper abdomen) from baseline (pre-procedure) to following completion of the four-week procedure administration phase (study endpoint). It was pre-determined that a subject would be considered a study success if he or she attained a 3.0 inch or greater reduction in total combined circumference across this primary evaluation period. It was also pre-determined that the study would be considered an overall success if the proportion of individual subject successes in the test (active procedure) group was at least 40% greater than the proportion of individual subject successes in the placebo (sham procedure) group.

71.43% of subjects who received the active study procedures with the Erchonia® Obesity Laser attained a decrease in combined circumference measurements of 3.0 inches or greater compared with 12% of subjects who received the 'fake' (placebo) laser procedures. A Fischer's Exact Test for two independent proportions found this difference of 59.43% between subject procedure groups to be statistically significant at $p<0.00005$.

[figure not shown]
The mean change in combined circumference measurement for subjects who received the active study procedures with the Erchonia® Obesity Laser was a decrease of 4.14 inches, while the mean change in combined circumference measurements for subjects who received the 'fake' (placebo) laser procedures was a decrease of 0.71 inches. A t-test for two independent samples found the mean change in combined circumference measurements from baseline to study endpoint for test (active procedure) group subjects to be significantly greater than that for placebo (sham procedure) group subjects, at $p<0.0001$.

Table 3 and Chart 1 below show the mean change in combined circumference measurements across the four study evaluation points for test and placebo group subjects.

Table 3: Mean total circumference measurements (ins.) across evaluation points

	Test Group	Placebo Group
Baseline	123.35	122.81
Midpoint (week 2)	120.86	122.09
Endpoint (week 4)	119.21	122.10
2 Weeks Follow-up	118.73	122.08

Chart 1: Mean change in total circumference measurements (ins.) at each study evaluation point relative to baseline

For test subjects, total circumference measurements decreased progressively from baseline at each of the three subsequent evaluation points culminating in a mean decrease of 4.62 inches by 2 weeks post-procedure evaluation. For placebo subjects, the magnitude of the change was constant for all three subsequent evaluation points relative to baseline, indicating lack of any change in total circumference measurements beyond week 2 evaluation relative to baseline. Additionally, the magnitude of the changes relative to baseline for placebo group subjects were notably less than the respective changes for test group subjects relative to baseline. Considered together, these findings support progressive effectiveness of the Erchonia® Obesity Laser procedures over time compared with placebo.

At completion of study procedure administration, the subject was asked to rate how satisfied he or she was with any overall perceived change in the appearance of the hips-waist-upper abdomen area using the following five-point scale: Very Satisfied; Somewhat Satisfied; Neither Satisfied nor Dissatisfied; Not Very Satisfied; Not at All Satisfied. 79% of test group subjects reported being 'Satisfied' ('Very Satisfied' or 'Somewhat Satisfied') with the study outcome compared with 16% of placebo subjects.

ADVERSE EVENTS

No adverse event occurred for any subject throughout duration of the clinical study. There was no change in skin markers in the treated body areas, and no notable deviation from baseline diet, exercise or concomitant medication use for any study subject.

CONCLUSION

The Erchonia® Obesity Laser is an effective tool for reducing circumference measurements of the hips-waist-upper abdomen in individuals with Body Mass Index (BMI) between 30 kg/m² and 40 kg/m² over a 4-week period.

STUDY DESIGN

This clinical study is a prospective open-label design with post-study independent blinded outcome analysis to evaluate the efficacy of the Erchonia® CFL Laser in providing noninvasive fat reduction in the submental area. As such, all enrolled subjects will receive active study treatments, and therefore, randomization to procedure group is not applicable.

STUDY BLINDING

As all subjects in this study will receive active procedure administrations with the Erchonia® CFL, neither subjects nor treating investigators will be blinded.

However, study outcome assessments, including primary study success determination, will be blinded through use of three (3) Independent Blinded Evaluators who will assess the study primary efficacy outcome through evaluation of coded, deidentified photographic images of subjects' submental regions' before (pre-treatment) treatment and 12 weeks after treatment (Week 16 Endpoint) that are provided in randomized order post-study endpoint. The digital photographs will be presented to each Independent Blinded Evaluator in blinded coded randomized fashion, with randomization of photograph presentation order additionally occurring across test sites. Each Independent Blinded Evaluator will perform and record the study primary efficacy outcome assessment independently of each other, without input, consultation, comparison of determinations, or any other form of interaction or communication with each other during the assessment process. The Independent Blinded Evaluators will not have otherwise been involved with any aspect of study design or execution.

Randomization of order of subject post-hoc photo presentation will be attained using computer generation sequence methodology (www.randomization.com) ensuring that the randomization methodology and the generated allocation sequence is concealed from the Independent Blinded Evaluators. Each computer-generated randomization sequence is unique and will therefore not be able to be replicated.

INDEPENDENT BLINDED EVALUATORS

Independent Blinded Evaluators participating in this study will be licensed and qualified physicians such as MD's, DO's, Dermatologists, Plastic surgeons, Cosmetic surgeons, and Board-certified weight loss physicians who are trained and experienced in visualizing, treating, and observing for change in submental fat.

SUBJECTS

Subject Sample

Subjects will be males and females 18 to 65 years of age who present with visible fat bulges in the submental area and who subsequently satisfy all qualification criteria.

Sample Size

There will be 35 qualified subjects enrolled in this study.

Rationale for Sample Size

In consideration of the primary efficacy outcome assessment, a clinically important outcome is pre-established as at least 2 of the 3 Independent Blinded Evaluators correctly identifying a subject's Pre-Treatment and Post-Treatment (study Endpoint of Week 16 – 12 Weeks Post-Treatment End) photographic images of the submental region, with study success defined as a Responder Rate of 80% or greater.

Consequently, the planned sample size to provide sufficient power for a statistical comparison of the proportion of treatment responders (P) versus a reasonable cutoff (P0) is based on a power calculation utilizing the (one proportion) binomial exact test based on the following assumptions.

- $H_0: P \leq P_0$ versus $H_a: P > P_0$
- Type I error rate: $\alpha = 0.025$
- Power = 90%
- Population proportion under the null hypothesis: $P_0 = 0.80$
- Population proportion under the alternative hypothesis: $P = 0.50$
- Total N = 30 study participants

To account for a potential 15% subject attrition rate, a total of 35 subjects will be enrolled.

Recruitment

Subjects will be recruited from among:

- (i) The test site's pool of existing and new clients
- (ii) Subjects who respond to the recruitment materials found in **Appendix C**.

Compensation

A subject will not be offered money or any other form of compensation to participate in the study; however, he or she will also not be charged for the cost of the study procedures with the Erchonia® CFL or for the cost of any other directly-related evaluations or measurements that occur as part of his or her participation in the study.

STUDY PROCEDURE

STUDY TEST BATTERY

The following is a list of the study measurement tools to be used in this study. For each study phase, the precise tools from this list that will be employed will be specified.

BODY MASS INDEX (BMI): BMI is calculated as the ratio of the subject's weight in kilograms (or pounds) to the square of the subject's height in meters (or feet).

PHOTOGRAPHS: Subjects will be photographed in a seated position. High-resolution digital images will be taken from the frontal view and from each lateral view (right and left side) at each evaluation visit. Photographs will be acquired using a standardized photography set-up (Apple iPad 12 [12-megapixel], ring light tripod) to ensure consistency, and will be taken in a standardized manner in the same room under the same lighting conditions, with effort made for the images to be taken by the same individual, with the same system settings fixed at the same location, with all subjects situated at the same distance from the lens for each photograph. At each post-baseline visit, the photographer will refer to the baseline photographs to ensure consistency in subject positioning and exposure. These same protocols will be employed across all study test sites.

Detailed instructions and the protocol for capturing the photographs are contained in **Appendix B: Photograph Methodology Instruction Sheet**.

SKINFOLD MEASUREMENT: The caliper measurement process involves pinching the tissue within the treatment area to obtain the measurement, thereby folding the tissue, and doubling the fat layer thickness. Measurements are taken with subjects standing in a neutral position, with the

head slightly lifted yet allowing the skin of the neck to remain loose such that a vertical fold is created above the hyoid bone.

The total measured value (mm) will be halved to reflect a single fat layer change and will not take into account the fold of tissue during the measurement process.

DEMOGRAPHICS: Age, gender, ethnicity, and Body Mass Index (BMI)

SUBJECT SATISFACTION WITH STUDY OUTCOME: The subject is asked to rate how satisfied he or she is with any change in the appearance of the fat pad under the chin following completion of the laser administration procedure with the Erchonia® CFL by using the 5-point Likert scale below to respond to the following question:

“Overall, how satisfied or dissatisfied are you with any change in the appearance of the fat pad under your chin following the study procedures with the study laser device?”

- Very Satisfied
- Somewhat Satisfied
- Neither Satisfied nor Dissatisfied
- Not Very Satisfied
- Not at All Satisfied

STUDY PROCEDURES

PRE-TREATMENT ACTIVITIES

The pre-treatment activities will be conducted at the test site prior to administration of the initial study treatment with the Erchonia® CFL.

SIGNING OF INFORMED CONSENT FORM

The investigator will commence by presenting and reviewing in detail the items in the informed consent form with the individual and answer any questions. To proceed, the individual must willingly sign the informed consent form.

ASSIGNMENT OF SUBJECT ID

The subject will be assigned a unique subject identification number based upon his or her order of entry into the study.

Additional information about the informed consent and subject ID number assignment is contained in a later section of the protocol titled, “SAFETY AND CONFIDENTIALITY ISSUES.”

STUDY QUALIFICATION EVALUATION: INCLUSION/EXCLUSION CRITERIA

INCLUSION CRITERIA

To be eligible for participation in this study, a subject must satisfy each of the following.

- Male or female 18 to 65 years of age, inclusive.
- Submental and submandibular skin fold thickness > 1cm (measured by caliper).
- Subject agrees to maintain his/her weight (i.e., within 5%) by not making any major changes in diet or exercise routine during the course of the study.

- Subject agrees to abstain from partaking in any treatment to promote body contouring and/or weight loss during the course of study participation. Such treatments include, but are not limited to:
 - over-the-counter and/or prescription medications; dietary/herbal supplements and appetite suppressants.
 - weight loss programs/diet plans.
 - surgical procedures for sculpting of the chin fat pad/weight loss, e.g. submental lipectomy, lap bands
- Subject has signed a written informed consent form.

EXCLUSION CRITERIA

A subject who satisfies any of the following criteria will be excluded from study participation:

- Evidence of any cause of enlargement in the submental area other than localized subcutaneous fat, such as swollen lymph nodes or ptotic submandibular glands.
- Treatment with dermal fillers, radiofrequency or laser procedures, or chemical peels in the neck or chin area (below the mandible) within the past 6 months.
- Botulinum toxin or other aesthetic drug injections within the neck or chin area (below the mandible) within the past 6 months.
- History of a fat reduction procedure (e.g., liposuction, surgery, lipolytic agents, etc.) or implant in or adjacent to the area of intended treatment.
- Any dermatological conditions, such as scars in the location of the treatment area that may interfere with the treatment or evaluation.
- Active implanted device such as a pacemaker, defibrillator, or drug delivery system.
- Pregnant or intending to become pregnant in the next 6 months.
- Currently enrolled in a clinical study of an unapproved investigational drug or device.

PRE-TREATMENT EVALUATIONS

The following pre-treatment measures will be recorded prior to commencement of the treatment administration phase (prior to treatment administration #1).

BASELINE VARIABLES

- Subject Demographics
- Body Mass Index (BMI) Calculation
- Concomitant Medication and Therapy Use

PRE-TREATMENT OUTCOME ASSESSMENTS

- Photographs
- Skinfold measurements (mm).

The Pre-Treatment photographs and skinfold caliper measurement will serve as the Baseline data set for relative assessment of post-treatment change.

TREATMENT ADMINISTRATION PHASE

TREATMENT ADMINISTRATION PROTOCOL

- The treatment administration phase of the study may commence on the same day as the pre-treatment measurements are recorded.
- The treatment administration phase will extend over four consecutive weeks.
- Each subject will receive eight (8) treatment administrations with the Erchonia® CFL across the consecutive four-week treatment administration phase; two treatments per week; each one at least two days apart.
- Each treatment will take place at the investigator's test site.
- The treatment administration protocol for each session is as follows:
 1. The subject enters the treatment administration room and lays comfortably on a treatment table.
 2. The subject is correctly fitted with the safety glasses.
 3. Utilizing the flexible laser stand, the investigator positions the Erchonia® CFL at a distance of about 3-4 inches from the surface of the skin, the device itself never touches the skin surface.
 4. The device is aligned so that the emitted laser light beams that cross forming an "X" is centered on the fat pad under the chin.
 5. The Erchonia® CFL treatment will run for fifteen (15) continuous minutes and will stop once the treatment time is at 0:00. Once the "Time Remaining" display reaches 0:00 the treatment is complete, the laser lights and the laser indicator light will turn off.
 6. After the Erchonia® CFL is turned off, the subject removes the safety glasses and leaves the treatment administration room.

TREATMENT ADMINISTRATION RECORD

Following the completion of each treatment with the CFL laser, the investigator will record the following:

- Number of treatment administrations
- Date
- Investigator signature
- Adverse event (if applicable).

POST-TREATMENT ACTIVITIES

WEEK 4 EVALUATION: TREATMENT ENDPOINT: AT THE TIME OF TREATMENT PROTOCOL END

Following the final treatment at completion of the 4 weeks of study treatment administrations with the Erchonia® CFL, the following will be recorded on the provided Case Report Forms.

- Photographs
- Skinfold caliper measurements (mm)
- Body Mass Index (BMI) Calculation
- Subject Satisfaction with Study Outcome

WEEK 16 EVALUATION: STUDY EFFICACY ENDPOINT: 12 WEEK POST TREATMENT ADMINISTRATION END

Twelve (12) weeks following the completion of the 4-week treatment administration protocol, the following will be recorded on the provided Case Report Forms. These recordings will form the study endpoint data set from which change from baseline will be evaluated with respect to

assessing study outcome.

- Photographs
- Skinfold caliper measurements (mm)
- Body Mass Index (BMI) Calculation
- Subject Satisfaction with Study Outcome

ADVERSE EVENTS

At each evaluation point throughout the clinical study, and at any other time throughout the duration of the clinical trial that is necessary, any and all potential adverse events reported by a subject or observed by an investigator will be recorded on the case report form, and subsequently evaluated by a suitably qualified independent reviewer for determination of relationship to the study treatment and whether or not any corrective action needs to be taken. All potential adverse events recorded will be appropriately reported to the governing IRB, as applicable.

It is unlikely and not expected that any adverse events will result from implementation of this clinical study protocol. Prior clinical trials using low level laser light have not typically yielded any adverse events or reactions. However, potential adverse events that may feasibly occur from application of the Erchonia® CFL include, but are not necessarily limited to: skin irritation, discoloring, rash, indentations and infection.

PRIVACY AND CONFIDENTIALITY

Records for each subject in this clinical study will be maintained in separate files in a locked filing cabinet at the respective test site. The investigator at the test site will be responsible for ensuring that all records for a subject pertaining to his or her participation in the clinical study are stored in that subject's file at all times other than when information is being recorded on them.

Copies of all of the subject case report forms will be made and supplied to Erchonia Corporation who will maintain these copies in a separate clinical study file that is kept in a locked filing cabinet at their premise. The original records will be maintained at the respective test sites.

Subjects' identities will be kept confidential by assigning each subject a subject ID upon acceptance into the study. The subject ID will comprise the investigator's first and last name initials followed by a three-digit number determined according to the subject's order of entry into the study. The first test site will be assigned a range of numbers from 001 to 100. The second test site will be assigned a range of numbers from 101 to 200. For example, the eighth subject to be enrolled at the first test site under PI [name] would have a subject ID of JB008. Neither the study Sponsor, Monitor, biostatistician, Independent Blinded Evaluators, nor any other pertinent party will receive any additional identifying information about a subject and will therefore have no way of linking a Subject ID to a particular subject and his or her study results.

STATISTICAL ANALYSIS PLAN

STUDY POPULATIONS

The following two study populations will be evaluated:

1. Intent-to-Treat (ITT) Population

Primary analysis of efficacy will be according to the intent to treat (mITT) analysis, including all consented and enrolled subjects.

2. Per Protocol Population

Secondary analysis of efficacy to confirm the findings of the primary analysis will be conducted on the Per Protocol population, comprised of all subjects who completed the study per protocol inclusive of all assessment visits and activities and the full 4-week, 8-treatment administration protocol.

3. Handling of Missing Data

Missing data values will be imputed using regression analysis imputation methodology under the assumption of the data missing at random (MAR), provided that the assumption of the data being MAR can be supported as has been found through prior Erchonia studies and demonstrated through the following means, the first two of which are already established by the study design:

1. As there is no placebo group in this clinical study design, subjects are aware that they are receiving active study treatments, and therefore, subject lost to follow up cannot be attributed to potential study unblinding.
2. The primary outcome assessment is a binary response responder rate format determined by Independent Blinded Evaluators that is therefore independent of individual subject variables.
3. Comparison of demographics for the group of subjects with missing data to the entire subject ITT group will be performed to demonstrate comparability.
4. Comparison of the primary outcome assessment for the group of subjects with missing data to the entire subject ITT group will be performed to demonstrate comparability.

Given that the assumption of the data being MAR is supported, the missing data will be imputed using the regression imputation methodology with known variables approach wherein the regression equation is employed to calculate the marginal or conditional average for each individual subject's missing value based on the known Baseline value of the missing variable value being imputed for that subject if available or if not available, on the known Baseline value for other subject(s) with comparable demographic profiles.

DEMOGRAPHICS

The following subject demographics collected at the Pre-Treatment assessment visit will be analyzed descriptively as means, standard deviations, medians, and range (minimum, maximum) for continuous data and as number (N) and percentages(%) of the total sample for categorical data and presented in table format, as applicable for the ITT subject population.

- Gender
- Age

- Ethnicity
- Body Mass Index (BMI): weight (kg), Height (inches / meters).

BASELINE SKINFOLD MEASUREMENTS

Baseline skinfold measurements (mm) and submental skinfold thickness (mm) measurements will be presented descriptively in table format as means, standard deviations, medians, and range (minimum, maximum) for the ITT subject population.

BASELINE CONCOMITANT MEDICATION USE

Recorded baseline concomitant medication use will be presented in table format as number (N) and percentage (%) of totals and reported as individual medications and further groups by indication for use for the ITT subject population.

PRIMARY EFFICACY OUTCOME ANALYSIS

The primary goal of this study is to determine if the treatment effect of the Erchonia© CFL can affect the appearance of visible fat bulges in the submental area.

PRIMARY STUDY SUCCESS EVALUATION CRITERIA

The primary efficacy outcome for this clinical study is established as the proportion of accurately identified subject pre- and post-treatment photographs by at least two of the three Blinded Independent Evaluators.

In consideration of this primary efficacy outcome assessment, a clinically important outcome is defined as at least 2 of the 3 Independent Blinded Evaluators (i.e., 2 out of 3, or 3 out of 3) correctly identifying the order of a subject's Pre-Treatment (Baseline) and Week 16 (Endpoint) 12 Weeks Post-Final Treatment photograph for 80% or more of subjects.

This clinically important minimum upper limit criteria of 80% was selected to be identical to the respective primary efficacy endpoint assessment parameters from the clinical studies for the ZELTIQ CoolSculpting System (K151179), and SculpSure (K171992) whose outcomes successfully supported FDA clearances for the same indication as intended to be supported by the outcome of the current clinical study protocol.

HYPOTHESES

The null and alternative hypotheses for the Primary Efficacy Endpoint are the following:

Null Hypotheses: The overall responder rate will be less than 80%.

$$H_0: \mu A < 80\%$$

Alternative Hypothesis: The overall responder rate will be 80% or greater.

$$H_0: \mu A \geq 80\%$$

PRIMARY EFFICACY OUTCOME ANALYSIS POPULATION

Determination of primary efficacy outcome success will be according to analysis of the outcome

for the subject ITT population as the primary analysis population. Primary efficacy outcome success will also be evaluated for the study Per Protocol population as a secondary analysis to provide support for and confirm the outcome of the primary analysis performed on the ITT subject population.

PRIMARY EFFICACY OUTCOME STATISTICAL EVALUATION

Primary study efficacy will be evaluated at Week 16, 12 Weeks Post-Final Treatment administration relative to Baseline (Pre-Treatment).

Primary efficacy outcome success will be evaluated via Responder Rate Analysis, wherein:

- (i) An individual subject is defined as a Study Responder if at least 2 of the 3 Independent Blinded Evaluators correctly identify the subject's post-treatment photograph, and
- (ii) Overall study success is defined as a minimum responder rate of 80%.

To determine primary efficacy outcome success, the following process will be followed:

1. The percentage of individual Study Responders will be calculated to determine the responder rate.
2. If the calculated responder rate is 80% or greater ($\geq 80\%$), it will be concluded that primary efficacy success has been demonstrated.
3. If the calculated responder rate is less than 80% ($< 80\%$), it will be concluded that primary efficacy success has not been demonstrated.

SECONDARY EVALUATIONS The secondary efficacy outcomes of submental skinfold and submental skinfold thickness, and subject satisfaction with treatment outcome will be assessed for each of the ITT and Per Protocol analysis populations, as applicable. As these secondary outcomes are provided as supportive evidence for the primary efficacy outcome only and the Sponsor **does not intend to seek clearance for any claims based on findings of these secondary efficacy outcomes**, the findings will be presented descriptively only as means, standard deviations, medians, and ranges for the continuous data and as number (N) and percentage (%) of the total for categorical data and will be presented in table and chart format, as applicable. Statistical analysis of change will not be performed.

- Submental skinfold and submental skinfold thickness measurements (mm) data will be recorded at each of the Pre-Treatment (Baseline), Week 4 (Treatment End), and Week 16 (12 Weeks Post-Treatment End) visits.
- Subject satisfaction with study outcome ratings will be recorded at each of the Week 4 (Treatment End) and Week 16 (12 Weeks Post-Treatment End) visits.

'Positive' subject satisfaction with treatment outcome response is predefined as the sum of 'Very Satisfied' and 'Somewhat Satisfied' responses.

- Additionally, comparison of the mean, standard deviation, median, and range of Body Mass Index (BMI) recording at each of Pre-Treatment (Baseline), Week 4 (Treatment End), and Week 16 (12 Weeks Post-Treatment End) visits will be compared descriptively to confirm that changes in body BMI did not contribute to the study outcome.

SAFETY ANALYSES

Safety analyses will be based on all subjects who signed informed consent and were enrolled in the study.

Safety will be assessed by evaluating observed and/or reported adverse events.

INFORMED CONSENT

- Informed consent will be an agreement between the individual investigator and each subject, having the capacity to understand and make an informed decision. Consent will be obtained prior to each potential subject's participation in this study.
- Each subject participating in this study will be made aware of the fact that his or her participation involves research and the intent of the research, the expected duration of participation and a description of the procedures that will be followed.
- Each subject will be made aware of the reasonably expected benefits he or she might receive, as well as any risks or potential discomfort that are involved.
- Each subject will also be made aware of alternative treatments available to him or her.
- Each subject will be made aware that his or her records will remain confidential, but that the FDA and the IRB has the right to inspect his or her records.
- Each subject will be told that his or her participation in the study is voluntary, without force or influence from the investigator or sponsor.
- Each subject will be given the name and method of contacting the appropriate person(s) to answer questions about the research and in the event of a research-related injury.

The Subject Informed Consent Form can be found in **Appendix D**.

CASE REPORT FORMS

The case report forms that will be used to collect the data from each subject in this study can be found in **Appendix E**.

END OF DOCUMENT

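### The sample-size inputs contradict their own hypotheses, so the stated 90% power is wrong as written; swapping them still does not give the power of the 80% success rule

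*Combined protocol and SAP*

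**What the plan says.** Under Rationale for Sample Size, the protocol says the planned size "is based on a power calculation utilizing the (one proportion) binomial exact test". The hypotheses are "H_0: P \leq P_0$ versus $H_a: P > P_0", with a type I error rate of 0.025. The two proportions follow on separate labelled lines: "Population proportion under the null hypothesis: $P_0 = 0.80" and "Population proportion under the alternative hypothesis: $P = 0.50". The section claims 90% power with 30 participants and enrols 35 to allow for 15% attrition.

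The statistical analysis plan, under Hypotheses, places the boundary at the same value: "Null Hypotheses: The overall responder rate will be less than 80" percent. Under Primary Efficacy Outcome Statistical Evaluation the decision rests on the observed proportion: "Overall study success is defined as a minimum responder rate of 80" percent. No test, p-value or confidence bound enters that decision. The primary population is ITT, defined as all consented and enrolled subjects, with imputation of missing values.

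Study Blinding describes the assessment: three evaluators view coded pre-treatment and Week 16 images "that are provided in randomized order post-study endpoint". A subject is a responder if at least two of the three evaluators identify the post-treatment photograph correctly.

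**The concern.** An alternative of 0.50 cannot satisfy Ha: P > 0.80. A test built to detect rates above 0.80 has essentially no chance of rejecting when the true rate is 0.50, so the stated hypotheses, inputs and power cannot all be right.

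The natural guess is that the two proportions were transposed. Even then, the powered test (is the rate above 0.50?) differs from the rule that decides the study (is the observed rate at least 0.80?). The power of the first says nothing direct about the second.

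This section is the only justification for the number of subjects in a single-arm study meant to support a 510(k) submission. A reader who sees 90% power will take it as the chance that an effective device meets the study's success definition. On no reading of the two sections is it that.

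**Working it through.** **Inputs.** From Rationale for Sample Size: exact one-proportion binomial test, Ha: P > P0, alpha 0.025, P0 = 0.80, P = 0.50, N = 30 evaluable, 35 enrolled. From the statistical analysis plan: success if the observed rate is at least 80%, that is 0.80 × 30 = 24 or 0.80 × 35 = 28 responders.

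**Method.** For an upper-tail test, the critical count r is the smallest value with P(X ≥ r | N, P0) ≤ 0.025. Power is P(X ≥ r | N, P), with X binomial.

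**1. The plan's figure as printed.**
- N = 30, P0 = 0.80: P(X ≥ 28) = 0.0442 and P(X ≥ 29) = 0.0105, so r = 29. Power at 0.50 is P(X ≥ 29 | 0.50) = 2.9 × 10⁻⁸.
- N = 35: P(X ≥ 32) = 0.0605 and P(X ≥ 33) = 0.0190, so r = 33. Power at 0.50 is 1.8 × 10⁻⁸.

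The stated 90% is not reproduced.

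**2. Where 90% could have come from.**
- Printed proportions, rejecting in the lower tail, N = 30: P(X ≤ 18 | 0.80) = 0.0095 and P(X ≤ 18 | 0.50) = 0.8998. This matches 90%, but it is power to show that the rate is *below* 80%, the opposite of the stated alternative.
- Proportions swapped (P0 = 0.50, P = 0.80), N = 30: P(X ≥ 21 | 0.50) = 0.0214, so r = 21, and P(X ≥ 21 | 0.80) = 0.9389.
- Swapped, N = 35: P(X ≥ 24 | 0.50) = 0.0205, so r = 24, and P(X ≥ 24 | 0.80) = 0.9656.
- Swapped power is 0.910 at N = 28, 0.892 at N = 29 and 0.939 at N = 30, and it stays above 0.90 for every N from 30 to 40.

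The documents do not show which calculation was run.

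**3. What 0.50 may stand for.** If each evaluator guesses between two photographs in random order, each is correct with probability 0.5. Then P(at least 2 of 3 correct) = 3 × 0.5³ + 0.5³ = 0.375 + 0.125 = 0.50. This is an inference; no section of the documents says it.

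**4. The success rule compared with the swapped test.**

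| | N = 30 | N = 35 |
|---|---|---|
| Swapped test rejects at | ≥ 21 (70.0%) | ≥ 24 (68.6%) |
| Success rule requires | ≥ 24 | ≥ 28 |
| Swapped test, power at 0.80 | 93.9% | 96.6% |
| Success rule met at true rate 0.80 | 60.7% | 59.9% |
| Beats chance but fails the rule, at 0.80 | 33.2% (21–23) | 36.6% (24–27) |
| True rate at which the rule is met 90% of the time | about 86.5% | about 86.2% |

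The fifth row is the difference of the two above it: 0.9389 − 0.6070 = 0.3319 and 0.9656 − 0.5993 = 0.3663.

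**5. If 0.80 is kept as the tested null.** The true rates here are assumptions, since the documents give none above 0.80.
- N = 30 (r = 29): power 18.4% at 0.90 and 55.4% at 0.95.
- N = 35 (r = 33): power 30.6% at 0.90 and 74.6% at 0.95.
- The first N to reach 90% is 137 at 0.90 and 48 at 0.95. Exact power dips below 90% again beyond those values and holds only from 149 and 55.
- The observed-80% rule does not test this null at 0.025. With a true rate of 0.79, inside the plan's null, it declares success with probability 55.3% at N = 30.

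**The case against.** The strongest reply is that this is a labelling slip with little practical effect. With the proportions swapped, N = 30 is the size from which exact power stays above 90% across the range checked, which fits 90% being a design target. The success rule is stricter than that test, with a false-success probability under guessing of 0.0007 at 24/30 and 0.0003 at 28/35, so a result of 21 to 23 of 30 falls short of a deliberately higher bar. The 60% figure also applies only if the truth sits exactly at the threshold; at an assumed true rate of 0.90 the rule is met 97.4% of the time at N = 30. The documents call 0.80 a minimum and never an expected rate.

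Much of this stands. The sample size is adequate for beating chance, and the stricter rule mainly puts the sponsor at risk. It is also fair that the swap is inferred and that the printed inputs in the lower tail come closer to 90% than the swapped ones. None of it reconciles the text. The printed hypotheses and inputs do not give the printed power. If 0.80 becomes the design alternative, it is the rate at which the plan claims its power, and the success rule has about 60% there. If 0.80 stays the null, no alternative is stated at all. That the 80% threshold was taken from earlier device studies explains the threshold, not the power inputs.

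**Conclusion.** The concern holds. As written, the power at the stated alternative is effectively zero. With the inputs swapped it is 93.9% (N = 30) or 96.6% (N = 35), but that is power to beat 0.50. The probability of meeting the plan's success definition at a true rate of 0.80 is 60.7% or 59.9%. Because the primary population includes everyone enrolled, 28/35 is the relevant count if 35 subjects enrol.

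These results rest on exact binomial calculation and on reading alpha 0.025 as one-sided, as the stated hypotheses imply. The transposition and the guessing-rate meaning of 0.50 are inferences. The contradiction does not depend on them.

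**What to change.** The sponsor should first establish which calculation was run and which null is intended, then edit Rationale for Sample Size and the Hypotheses and Statistical Evaluation text together.

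**If 0.50 is the null.**
- In Rationale for Sample Size, state P0 = 0.50 and say that it is the guessing rate for at least two of three correct choices. State P = 0.80, Ha: P > 0.50 and one-sided alpha 0.025.
- Replace the 90% figure with exact power of 93.9% at N = 30 (critical count 21) and 96.6% at N = 35 (critical count 24), labelled as power to beat chance.
- In the analysis plan, align the hypotheses with that null and present the observed-80% rule as a separate success criterion. Report that it is met with probability 60.7% (24/30) or 59.9% (28/35) at a true rate of 0.80, and 90% only at about 86.5% or 86.2%.

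This costs a few lines and no extra subjects.

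**If 0.80 remains the tested null.** Withdraw the 90% claim at N = 30, or state and justify an assumed true rate above 0.80 and re-size. The smallest evaluable N reaching 90% is 137 at an assumed 0.90 or 48 at an assumed 0.95 (149 or 55 if power is to stay above 90%). Applying the plan's 15% attrition to the first pair gives 137/0.85, or 162 enrolled, and 48/0.85, or 57 enrolled.
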